## 6 Study Design

### 6.1 General Design

This study is a multi-center, Phase I/II, dose escalation, open-label study to determine the safety of TFP in adult subjects with DBA and RBC-transfusion-dependence. A 3+3 dose escalation regimen will be used. The maximum time on study drug will be 21 days with a 1 week post-treatment follow-up period. It is expected that up to 24 subjects can be recruited and complete the study within 12-18 months. The dose escalation study design is shown in Figure 1:

- If 2 or more of the 6 subjects in Cohort B demonstrate toxicity  $\geq$  Grade 3, the study will be stopped, and 1 mg/day will be declared the MTD.
  - If  $< 2$  of the 6 subjects in Cohort B demonstrate toxicity  $\geq$  Grade 3 within 21 days of starting therapy, Cohort C will start.
3. Cohort C: Three subjects will receive TFP 5 mg PO daily.
- If there is no toxicity  $\geq$  Grade 3 at the end of the 21 days, Cohort D will start.
  - If 1/3 subjects in Cohort C demonstrates toxicity  $\geq$  Grade 3, an additional 3 subjects will be enrolled in Cohort C:
    - If 2 or more of the 6 subjects in Cohort C demonstrate toxicity  $\geq$  Grade 3, the study will be stopped, and 2 mg/day will be declared the MTD.
    - If  $< 2$  of the 6 subjects in Cohort C demonstrate toxicity  $\geq$  Grade 3 within 21 days of starting therapy, cohort D will start.
4. Cohort D: Three subjects will receive TFP 10 mg PO daily.
- If 0/3 subjects in Cohort D demonstrates toxicity  $\geq$  Grade 3, the study will be stopped, and 10 mg/day will be declared the MTD.
  - If 1/3 subjects in Cohort D demonstrates toxicity  $\geq$  Grade 3, an additional 3 subjects will be enrolled in Cohort D.
  - If 2 or more of the 6 subjects in Cohort D demonstrate toxicity  $\geq$  Grade 3, the study will be stopped, and 5 mg/day will be declared the MTD.
  - If  $< 2$  of the 6 subjects in Cohort D demonstrate toxicity  $\geq$  Grade 3 within 21 days of starting therapy, 10mg/day will be declared the MTD.

Each subject will undergo safety assessments as per the required schedule while on the study drug. All dosed subjects will be followed for an additional 1 week after discontinuing study drug (post-study safety follow-up). There will be no more than 6 subjects enrolled at any particular time.

Treatment will be discontinued for any subject if their Hb is > 12 gm/dL, not associated with RBC transfusions.

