## 7.2 Exclusion Criteria

Subjects who meet any of the following criteria will not be eligible to participate in the study:

1. Liver: aspartate aminotransferase (AST) > 5 x the upper limit of normal (ULN), alanine aminotransferase (ALT) >5 x ULN, or bilirubin > 5 x ULN.
2. Heart disease (New York Heart Association classification of  $\geq 3$ ; Appendix F).
3. History of angina.
4. Uncontrolled hypertension. If hypertension is considered clinically stable, systolic blood pressure must be <150 mmHg or diastolic blood pressure must be <100 mmHg.
5. Subjects currently responsive to corticosteroids for treatment of DBA.
6. Treatment with another investigational drug or device <56 days pre-study entry. Subjects who participated in an earlier cohort of this trial may participate in a subsequent cohort if (a) they meet all eligibility criteria, (b) did not experience any adverse effects  $\geq$  Grade 3 while on TFP, and (c) discontinued TFP  $\geq$  6 days (10 half-lives) prior to day 1 of the subsequent cohort.
7. Pregnant or lactating females.
8. Any history of severe allergic reaction requiring the use of epinephrine.
9. Known hypersensitivity to the study drug or other phenothiazines.
10. History or presence of extrapyramidal signs.
11. History of cancer.

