## **7.4 Subject Recruitment and Screening**

[name], is the PI and the Director and [name], PhD is a Co-Investigator and the Co-Director of the Diamond Blackfan Anemia Registry of North America, respectively. The DBAR is housed at the Feinstein Institute for Medical Research. There are over 750 subjects with Diamond Blackfan anemia enrolled in this Registry. Because of this, the investigators have access to the specific subject population required for this study. Subjects contact the DBAR periodically to inquire about available studies. Also the DBA Foundation (DBAF) (the family group) has access to most of the DBA families. The DBAF is highly supportive of the research and they also encourage the families to contact the DBAR for any available studies. We have prepared a study announcement (Appendix G) to inform the subjects of the study as we have for other studies in the past. This will be posted on the DBAF website (mostly visited by subjects/families) and our DBAR website (often visited by physicians as well as subjects/families) and has worked well previously.

Once informed consent is obtained from the subject, the following screening requirements will be performed:

- 1- Physical examination (including height at 1st visit only, weight, vital signs, blood pressure and neurological examination)
- 2- Hematology evaluation including RBC count, hemoglobin, hematocrit, absolute reticulocyte count, white blood cell count, absolute neutrophil count, and platelet count
- 3- Blood chemistry including blood urea nitrogen, creatinine, bilirubin [total and direct], aspartate aminotransferase [AST], and alanine aminotransferase [ALT])
- 4- If female, serum pregnancy test
- 5- Documentation of transfusion history for > 3 months before initiation of treatment

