occurrence, i.e. some are dose-related, while others involve individual subject sensitivity. Some adverse effects may be more likely to occur, or occur with greater intensity, in subjects with special medical problems, e.g., subjects with mitral insufficiency or pheochromocytoma have experienced hypotension following recommended doses of certain phenothiazines.

- Neuroleptic malignant syndrome (NMS) has been reported in association with antipsychotic drugs. Cardinal features of NMS are hyperpyrexia, muscle rigidity, altered mental status (including catatonic signs), and evidence of autonomic instability (irregular pulse or blood pressure). Additional signs may include elevated creatine phosphokinase, myoglobinuria (rhabdomyolysis), and acute renal failure. NMS is potentially fatal and requires symptomatic treatment and immediate discontinuation of neuroleptic treatment.

- Not all of the following adverse reactions have been observed with every phenothiazine derivative, but they have been reported with one or more and should be borne in mind when drugs of this class are administered: extrapyramidal symptoms (opisthotonos, oculogyric crisis, hyperreflexia, dystonia, akathisia, dyskinesia, parkinsonism) some of which have lasted months and even years—particularly in elderly subjects with previous brain damage; grand mal and petit mal convulsions, particularly in subjects with electroencephalogram abnormalities or history of such disorders; altered cerebrospinal fluid proteins; cerebral edema; intensification and prolongation of the action of central nervous system depressants (opiates, analgesics, antihistamines, barbiturates, alcohol), atropine, heat, organophosphorus insecticides; autonomic reactions (dryness of mouth, nasal congestion, headache, nausea, constipation, obstipation, adynamic ileus, ejaculatory disorders/impotence, priapism, atonic colon, urinary retention, miosis and mydriasis); reactivation of psychotic processes, catatonic-like states; hypotension (sometimes fatal); cardiac arrest; blood dyscrasias (pancytopenia, thrombocytopenic purpura, leukopenia, agranulocytosis, eosinophilia, hemolytic anemia, aplastic anemia); liver damage (jaundice, biliary stasis); endocrine disturbances (hyperglycemia, hypoglycemia, glycosuria, lactation, galactorrhea, gynecomastia, menstrual irregularities, false-positive pregnancy tests); skin disorders (photosensitivity, itching, erythema, urticaria, eczema up to exfoliative

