dermatitis); other allergic reactions (asthma, laryngeal edema, angioneurotic edema, anaphylactoid reactions); peripheral edema; reversed epinephrine effect; hyperpyrexia; increased appetite; increased weight; a systemic lupus erythematosus-like syndrome; pigmentary retinopathy; with prolonged administration of substantial doses, skin pigmentation, epithelial keratopathy, and lenticular and corneal deposits.

- Electrocardiogram changes, particularly nonspecific, usually reversible Q and T wave distortions, have been observed in some subjects receiving phenothiazine antipsychotics.

There have been occasional reports of sudden death in subjects receiving phenothiazines. In some cases, the cause appeared to be cardiac arrest or asphyxia due to failure of the cough reflex.

The effects of TFP on fertility or a fetus are not known. The side effects of TFP on newborns are also not known, therefore breastfeeding will not be allowed on the study. The subject will be removed from the study if she becomes pregnant during the study.

Adult subjects with DBA who are on chronic transfusion therapy may have iron overload despite iron chelation or due to non-compliance. Iron overload can lead to liver dysfunction (liver function test elevations initially and eventual fibrosis and cirrhosis), cardiac dysfunction (arrhythmias and eventual heart failure), and endocrine dysfunction (hypothyroidism, diabetes mellitus, growth hormone deficiency, hypogonadism, premature ovarian failure, etc.). If such dysfunction is documented but is adequately addressed, then these subjects will be eligible for this study. If any of these potential side effects occur for the first time while on the subject is on the study drug, the event will be treated as an adverse event (AE).

Subjects with DBA have RBC aplasia, thus necessitating transfusion therapy. As this is a bone marrow failure syndrome these subjects also can have other cytopenias including neutropenia and thrombocytopenia, and often pancytopenia (not necessarily consistent with aplastic anemia). The eligibility criteria for entry into the study allow mild abnormalities in all the cell lines, but subjects with severe cytopenia are ineligible.

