## 22.2 Appendix B: Diamond Blackfan Anemia Diagnostic Criteria

### Diagnostic Criteria

- Age less than 1 year
- Macrocytic anemia with no other significant cytopenias
- Reticulocytopenia
- Normal marrow cellularity with a paucity of erythroid precursors

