#### *Minor*

- Elevated erythrocyte adenosine deaminase activity
- Congenital anomalies described in “classical” DBA
- Elevated fetal hemoglobin
- No evidence of another inherited bone marrow failure syndrome

A diagnosis of “classical” DBA is made if all the diagnostic criteria are met. When there is a positive family history, an otherwise normal individual should be considered as having “non-classical” DBA if a mutation shared by affected family members is present. Anyone suspected of having DBA, but with insufficient diagnostic criteria, should be considered as having non-classical DBA if a reported mutation is present. A subject can be assigned as having a “probable” diagnosis, with a decreasing degree of certitude if:

- 3 diagnostic criteria are present along with a positive family history;
- 2 diagnostic criteria and 3 minor supporting criteria are present; or,
- positive family history and 3 minor supporting criteria are evident, even in the absence of diagnostic criteria.

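### Section 10's severe-cytopenia exclusion has no matching entry criterion, and Sections 6.1 and 15.4 can give different MTDs (10 or 5 mg/day) from the same Cohort D data

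*Combined protocol and SAP*

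**What the plan says.** **Cytopenia.** Section 10 describes what the entry criteria do: "The eligibility criteria for entry into the study allow mild abnormalities in all the cell lines, but subjects with severe cytopenia are ineligible". The criteria are in 7.1 and 7.2, and 7.2 opens with "Subjects who meet any of the following criteria will not be eligible to participate in the study". Together they give numeric limits for age, weight, creatinine clearance, Karnofsky score, liver tests and blood pressure. Screening includes "white blood cell count, absolute neutrophil count, and platelet count", with no cut-off attached.

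Two items reach blood counts through appendices:

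- Inclusion 3 cites Appendix B, whose diagnostic list includes "Macrocytic anemia with no other significant cytopenias" beside "Age less than 1 year". Appendix B also provides another route to the diagnosis: "Anyone suspected of having DBA, but with insufficient diagnostic criteria, should be considered as having non-classical DBA if a reported mutation is present".
- Inclusion 4 cites Appendix C, where transfusion dependence carries Hb below 8 gm/dL.

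**Escalation and stopping.** The Cohort C and D bullets in 6.1 count subjects with toxicity of Grade 3 or higher. For Cohort D the first bullet begins "If 0/3 subjects in Cohort D demonstrates toxicity" of that grade, and its consequence is that the study ends with 10 mg/day as the MTD. Section 15.4 Scenario 2 uses different triggers: more than one subject with extrapyramidal symptoms, tardive-dyskinesia signs (including early tongue movements) or neuroleptic malignant syndrome, or with the same SAE or Grade 3-or-higher treatment-emergent event attributed to TFP. Its rules c, d and e then stop the study and set the MTD at 1, 2 or 5 mg/day for Cohorts B, C and D.

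Section 2 sends the reader to Section 6 for the cohort stopping rules. Section 15.4 introduces its own list as the stopping rules. Neither says which prevails.

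**The concern.** On cytopenia, the risk section relies on a safeguard that the entry lists do not contain. It matters for this drug and this population. Section 10 says DBA patients can have neutropenia, thrombocytopenia and often pancytopenia, and it lists for the phenothiazine class "blood dyscrasias (pancytopenia, thrombocytopenic purpura, leukopenia, agranulocytosis, eosinophilia, hemolytic anemia, aplastic anemia". Someone working through 7.1 and 7.2 item by item would find nothing that excludes a subject with very low neutrophils or platelets. Section 10 also does not define what counts as severe.

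On the MTD, two sections attach the same consequences to different events. They diverge on extrapyramidal effects, which Section 2 expects to be the main dose-limiting toxicity with long-term use at antipsychotic doses. Section 10 adds that dystonia can appear within days of starting and at low doses. The Study Summary and Section 2 name the MTD as something the trial will determine, so one data set should lead to one value.

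**Working it through.** **1. The plan's own figure.** Four cohorts of at most six subjects give 4 × 6 = 24. The minimum is the first three subjects of Cohort A. Both match Section 14.1 and are not in dispute.

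**2. Entry criteria.** There are 10 inclusion and 11 exclusion items, 21 in all.

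- Items stating a neutrophil, white-cell or platelet limit: 0 of 21.
- Appendix C's Hb below 8 gm/dL is an upper bound that helps define transfusion dependence. It excludes nobody for cytopenia.
- Appendix B's cytopenia wording has no threshold. Its list also requires onset in infancy, so for adults it describes presentation and not counts at entry. The mutation-based non-classical route does not require it.

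**3. The two decision rules on the same data.** The extrapyramidal events below are taken as related to TFP, so the result does not depend on whether 15.4's causality condition covers them.

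| Outcome within one cohort | Section 6.1 | Section 15.4 Scenario 2 |
|---|---|---|
| D: 2 of 3 with Grade 1-2 extrapyramidal symptoms, 0 of 3 with Grade ≥3 | Study ends, MTD 10 mg/day | Study stops, MTD 5 mg/day (rule e) |
| C: same data | Cohort D opens at 10 mg/day | Study stops, MTD 2 mg/day (rule d) |
| D: 2 of 6 with different, non-neurologic, non-serious Grade 3 events | Study stops, MTD 5 mg/day | Not triggered |

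The first row gives two MTDs one dose level apart. The second gives a stop or a further cohort. The third is a mismatch only: 15.4 is silent there and declares no rival MTD.

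**4. Frequency, by assumption only.** The documents give no rate of extrapyramidal events at 10 mg/day or below. Suppose each of three subjects independently has probability p of a related Grade 1-2 extrapyramidal event and none has a Grade ≥3 event. The cohort then stays at three, and the chance of the first-row (or second-row) conflict is

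P(at least 2 of 3) = 3p²(1 − p) + p³

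| Assumed p | 3p²(1 − p) | p³ | Sum |
|---|---|---|---|
| 5% | 0.007125 | 0.000125 | 0.7% |
| 10% | 0.027 | 0.001 | 2.8% |
| 20% | 0.096 | 0.008 | 10.4% |
| 30% | 0.189 | 0.027 | 21.6% |

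These are per-cohort illustrations, not estimates. Section 3.4 reports side effects similar to placebo at 2-6 mg/day. At 15 mg/day it reports no difference in Parkinsonism or dystonia but more akathisia. These comparisons lean towards the low end but supply no value of p.

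**The case against.** **Section 10 is itself protocol text.** An investigator is bound by it, and the screening blood count supplies the data. That stands. A reader might infer that severely cytopenic subjects will therefore be dosed, or that the criteria contain no blood-count value at all. The documents support neither. The first assumes staff disregard Section 10, and the second overlooks the Hb value in Appendix C. What remains is an exclusion that is undefined and missing from the lists said to contain it.

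**Sequence may settle the order of the rules.** Section 15.4 acts as soon as a second subject is affected, while 3.5.1 holds the interim analysis after all three subjects have completed 21 days. A safety stop would then come before the escalation table. This is a sensible reading, and probably the intended one. It is not stated, however, and Section 2 directs readers to Section 6 for cohort stopping. Events first found at the Day 22 visit would reach both rules together. The last paragraph of 15.4 also restates the trial stop only for the lowest dose, which leaves some doubt about rules c to e.

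**The Grade 3 condition in 15.4 might cover its whole list.** If so, the conflict in the first two table rows disappears. The neurologic terms are listed separately, though, and include early tongue movements. Section 10 describes these as a possible early sign at which stopping may prevent the syndrome, so any grade is the natural reading.

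**Text not available.** Figure 1 and the 6.1 text on Cohort A and the start of Cohort B were not in the text reviewed. A cross-reference there could help. The Cohort C and D bullets print their own Grade 3 threshold.

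**Individual protection.** Scenario 1 stops treatment in each affected subject whichever section governs the cohort. That also stands.

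**Conclusion.** Both parts hold as internal inconsistencies. (a) The listed criteria do not implement the severe-cytopenia exclusion that Section 10 attributes to them: none of the 21 items limits neutrophils, white cells or platelets. (b) With two related Grade 1-2 extrapyramidal events among three subjects and no Grade ≥3 toxicity, Cohort D yields 10 mg/day under 6.1 and 5 mg/day under 15.4. In Cohort C the choice is between opening Cohort D and stopping at 2 mg/day.

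Part (b) rests on reading the neurologic triggers in 15.4 as applying at any grade, and on there being no precedence statement in the missing part of 6.1.

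A reader might put the Cohort C disagreement at five-fold (10 against 2 mg/day). That ratio compares a cohort being opened with a declared MTD, and a Cohort D opened under 6.1 could still end at a lower MTD. A reader might also conclude that the two sections need one merged definition of dose-limiting toxicity. The inconsistency does not require that, and merging would change the design. A single mild extrapyramidal event would newly force expansion, a mild event plus an unlike Grade 3 event would newly stop the trial, and an attribution condition could loosen 6.1.

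**What to change.** **Entry criteria.** Add one item to 7.2 excluding subjects below stated neutrophil and platelet limits, judged on the screening blood count already drawn. The sponsor must choose the values, since the documents offer none. Cost: amendment wording, and possibly a few candidates lost in a rare disease.

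**Precedence.** State in Section 2, 6.1 and 15.4 that both sets of rules apply in every cohort and that a Scenario 2 stop overrides the escalation and MTD bullets of 6.1. The next cohort opens, or 10 mg/day is declared the MTD, only if neither the 6.1 Grade ≥3 rule nor Scenario 2 is met. Leave the 6.1 count unchanged, with no attribution filter and no expansion for a single mild extrapyramidal event.

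Cost: amendment wording only, because the examinations, grades and relationship assessments are already collected. The declared MTD may be one level lower where mild extrapyramidal events recur, which 15.4 already requires. Before drafting, check the full 6.1 text and Figure 1 for an existing cross-reference.

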## **11 Potential Benefit to Subjects**

This is a safety study but the possible benefits from participation in this study include an improvement in the anemia of DBA and a decrease in the amount of transfusions needed by the subject. Since the study drug will be used for only 21 days, the risks to subjects are reasonable in relation to anticipated benefits, if any, to subjects, and the importance of the knowledge that may reasonably be expected to result. If the study drug is safe then it would introduce a new class of therapeutic agents to this rare population.

## **12 Research Related Harm/Injury**

You will receive medical care and treatment as needed from Northwell Health. However, you will be responsible for the costs of such medical treatment, directly or through your medical insurance or other forms of medical coverage. No money will be given to you for participation in the study.

## **13 Provisions to Protect Privacy Interests of Subjects**

There are over 750 subjects with Diamond Blackfan anemia enrolled in this Registry. Because of this, the investigators have access to the specific subject population required for this study. Subjects contact the DBAR periodically to inquire about available studies. Also the announcement (Appendix G) informs potential subjects of the study and we anticipate the subjects calling us if they are interested in the study. The consent will be mailed to the subject or handed to the subject at an office visit.

Once consented, subjects will be assigned a unique patient identification number (UPIN) that is used for entering data into the database. Protected health information (PHI) collected includes: name, address, contact numbers, email, and date of birth. Hard copies of study documents will be stored in a locked fireproof cabinet. Any research data that will be emailed will be encrypted.

## **14 Statistical Plan**

### **14.1 *Sample Size Determination***

This is a 4-Cohort, 3+3 study, and will therefore enroll a minimum of 3 patients and a maximum of 24 patients. Sample size power to detect a given effect does not apply.

### **14.2 *Statistical Methods***

All subjects who received at least one dose of study drug will be included for safety analysis. Demographics and baseline characteristics will be summarized by dose levels.

**Primary Endpoint(s)**

- All AEs (including non-serious and serious) will be summarized. Key laboratory results will be summarized using CTCAE grade.

**Secondary Endpoint(s):**

- Not applicable.

**14.3 Subject Population for Analysis**

There is no randomization for this study. All enrolled subjects will be included in the study analysis for the primary endpoint.

